6.2.3. Sensitivity Analysis

6.2.3.1. MMRM Analysis

A mixed-effects repeated measures (MMRM) analysis model will be implemented to estimate the mean change from baseline in the monthly average number of headache days of at least moderate severity for the overall 3 months treatment period and by each month to support the primary analysis.

Each patient's monthly number of headache days of at least moderate severity *during the 4-week period* will be calculated by formula (2) in Section 6.1 based on the e-diary responses for that

month. If a patient is early terminated or has intermittent missing days and has less than 10 days of e-diary entries for a month, that month value will be considered as missing as described in Section 4.5.

The MMRM model will include baseline value, treatment, sex, region, baseline preventive migraine medication use (yes/no), years since onset of migraines, month and treatment-by-month interaction as fixed effects, and patient in the repeated statement as a random effect. The unconstructed covariance structure will be used for the repeated observations within a patient. LS means for the treatment groups, LS means for the treatment differences (TEV-48125 - placebo), and corresponding 95% confidence intervals and associated p-values will be calculated by month and for the overall treatment period.

The following SAS code pertains to the MMRM analysis.

```
ODS OUTPUT DIFFS=XXX LSMEANS=XXX TESTS3=XXX;
PROC MIXED DATA=XXX METHOD=REML;
    CLASS USUBJID MONTH TREAT SEX BMU REGION;
    MODEL CHG=BASE YOD BMU SEX TREAT MONTH TREAT*MONTH/S;
    REPEATED MONTH / SUBJECT=USUBJID TYPE=UN R;
    LSMEANS TREAT TREAT*MONTH/PDIFF CL ALPHA=0.05;
RUN;
```

The LS means±SE of monthly change from baseline values estimated by MMRM will be plotted by month for each treatment group.

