6.2.2. Primary Analysis

The hypothesis testing for the primary analysis is:

$$H_o : \delta_1 = \delta_2 \quad vs \quad H_a : \delta_1 \neq \delta_2$$

where δ_1 and δ_2 are the estimates of mean change from baseline in the monthly average number of headache days of at least moderate severity for the TEV-48125 treatment group and the placebo group respectively. The estimated difference of TEV-48125 675/225/225 mg versus the placebo and TEV-48125 675/placebo/placebo mg versus the placebo will be tested following the pre-specified fixed sequence as described in Section 4.4.

An analysis of covariance (ANCOVA) method will be applied for the primary analysis. The model will include treatment, sex, region (Table 2), and baseline preventive migraine medication use (yes/no) as fixed effects; the baseline number of headache days of at least moderate severity and years since onset of migraines as covariates. The least square (LS) means for the treatment groups, LS means and corresponding 95% confidence intervals for the treatment differences (TEV-48125 – placebo), and associated p-values will be provided.

The following sample SAS code pertains to the primary analysis.

```
ODS OUTPUT DIFFS=XXX LSMEANS=XXX TESTS3=XXX;
PROC MIXED DATA=XXX;
    CLASS TREAT SEX BMU REGION;
    MODEL CHG=BASE YOD BMU SEX TREAT REGION/S;
    LSMEANS TREAT/PDIFF CL ALPHA=0.05;
RUN;
```

The normality of the residuals from the ANCOVA model will be checked using Shapiro Wilk's normality test. In case that the Shapiro Wilk's test has a p value ≤ 0.01 , Wilcoxon rank-sum test will be conducted as the primary analysis using SAS procedure NPAR1WAY for each active treatment group and placebo group. P value based on normal approximation from this procedure will be selected for the treatment comparison. The ANCOVA analysis will be performed as a supportive analysis.

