6.2.3.2. Analysis with Multiple Imputation Method

Multiple imputation (MI) method will be applied to impute the monthly missing data. The data will be processed by the following steps.

- If a patient has partial e-diary data (i.e., <10 days) for a month, that month value will be considered missing before the MI procedure.
- For the patients in the active treatment group who are early terminated with reasons of adverse event or lack of efficacy, they will be assigned to placebo group so their missing values will be imputed using data from the placebo treated patients
- Run SAS PROC MI procedure to create 10 complete datasets.
- Within each imputed data set, for a patient who has partial, say X ($X < 10$) days, e-diary data in a month, the monthly value will be replaced by

$$\sum(\text{observed days of at least moderate severity}) + (28 - X) * \text{imputed value} / 28$$
- The monthly average number of headache days of at least moderate severity **during the 12-week period** after the 1st dose of study drug will be the average of month 1, month 2 and month 3 values.

Each dataset will be analyzed using the same ANCOVA model as described in Section 6.2.2. The LS means and standard errors from each analysis will be output to a SAS data set. SAS MIANALYZE procedure will be used to generate the final LS means (±SE) for the treatment

groups and the treatment differences (TEV-48125 - placebo) as well as p-values associated with treatment differences. The 95% confidence intervals for the treatment differences will also be constructed.

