6.4.2. Exploratory Efficacy Analysis

6.4.2.1. Electronic Headache Diary Data

Cochran Mantel-Haenszel test stratified by baseline preventive migraine medication use (yes/no) will be implemented for analyzing the responder type of exploratory efficacy endpoints. The SAS Proc FREQ will be used to carry out this analysis.

An ANCOVA method defined in Section 6.2.2 and an MMRM model defined Section 6.2.3.1 will be implemented for the following exploratory endpoints analysis.

- mean change from baseline (28-day run-in period) in the monthly average number of headache days of any severity during the 12-week period after the 1st dose of study drug
- mean change from baseline (28-day run-in period) in the monthly average number of headache hours of any severity during the 12-week period after the 1st dose of study drug
- mean change from baseline (28-day run-in period) in the monthly average number of headache hours of at least moderate severity during the 12-week period after the 1st dose of study drug
- mean change from baseline (28-day run-in period) in the monthly average number of days with nausea or vomiting during the 12-week period after the 1st dose of the study drug
- mean change from baseline (28-day run-in period) in the monthly average number of days with photophobia and phonophobia during the 12-week period after the 1st dose of study drug

The 2 active treatment groups data will be combined to compare with the placebo group by ANCOVA method for analyzing the mean change from baseline in the number of migraine days during the 4-week period after the 1st dose of study drug.

Similar to the sensitivity analysis for the primary efficacy variable described in Section 6.2.3.1, an MMRM model will be implemented to estimate the mean change from baseline for the following endpoints by week after the 1st dose of study drug.

- mean change from baseline in the weekly number of headache days of at least moderate severity
- mean change from baseline in the weekly number of migraine days

LS means for the treatment groups, LS means and corresponding 95% confidence intervals for the treatment differences (TEV-48125 - placebo), and associated p-values will be calculated by week.

The LS means \pm SE of e-diary efficacy variables estimated by MMRM will be plotted by week for each treatment group.

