6.5. Subgroup Analysis

The ANCOVA analysis defined in Section 6.2.2 and MMRM analysis defined in Section 6.2.3.1 will also be applied to following subgroup populations analysis for the endpoints mean change from baseline in the monthly average number of headache days of at least moderate severity and number of migraine days.

- patients who are receiving or not receiving any concomitant preventive treatment
- patients who used topiramate for migraine in the past
- patients who used onabotulinumtoxinA for migraine in the past
- patients in different age group (18-45, >45 years old)
- patients in different race group (caucasian, non-caucasian)
- patients by sex

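### The MMRM code in SAP Section 6.2.3.1 leaves out region, which the text of the same section names as a fixed effect; the effect is small and no confirmatory test is affected

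*SAP*

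**What the plan says.** The text of SAP Section 6.2.3.1 states: "The MMRM model will include baseline value, treatment, sex, region, baseline preventive migraine medication use (yes/no), years since onset of migraines, month", and adds the treatment-by-month interaction. The code below it declares region in the CLASS line, "CLASS USUBJID MONTH TREAT SEX BMU REGION", but the model line is "MODEL CHG=BASE YOD BMU SEX TREAT MONTH TREAT*MONTH/S".

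The primary ANCOVA code in Section 6.2.2 does contain region: "MODEL CHG=BASE YOD BMU SEX TREAT REGION/S". The multiple-imputation analysis in Section 6.2.3.2 inherits that adjustment: "Each dataset will be analyzed using the same ANCOVA model as described in Section 6.2.2".

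The Section 6.2.3.1 model is reused for:

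- migraine days and acute-medication days (6.3.2);
- several exploratory diary endpoints and the weekly endpoints (6.4.2.1);
- the MSQOL domains (6.4.2.2);
- the subgroup analyses (6.5).

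The Preface ranks the SAP above the protocol. Nothing ranks the SAP's text above its code.

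**The concern.** Text and code define two different models for the same analysis. A programmer who copies the code fits an MMRM that does not adjust for region, the pooled form of the stratification factor country (Section 4.3, Table 2). The primary ANCOVA and the multiple-imputation analysis do adjust for it. A study report written from the SAP text could then describe a region-adjusted model that was never fitted, or the choice between the two could be made after unblinding.

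The MMRM supports the primary analysis, and its LS means are reported and plotted by month. For the weekly endpoints in Section 6.4.2.1 it is the only inferential method named. What could change is some precision in the treatment differences and the level of the LS means.

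**Working it through.** **Term-by-term comparison (Section 6.2.3.1)**

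| Effect in the text | In CLASS | In MODEL |
|---|---|---|
| Baseline value | continuous | BASE |
| Treatment | TREAT | TREAT |
| Sex | SEX | SEX |
| Region | REGION | **absent** |
| Baseline preventive use | BMU | BMU |
| Years since onset | continuous | YOD |
| Month | MONTH | MONTH |
| Treatment by month | – | TREAT*MONTH |

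**Does any confirmatory test use this model?** No. For the primary endpoint, "An analysis of covariance (ANCOVA) method will be applied for the primary analysis", with Wilcoxon as fallback. The secondary diary endpoints and HIT-6 use ANCOVA with the same fallback, and the 50% responder endpoint uses a Cochran-Mantel-Haenszel test (6.3.2). None of the 13 comparisons in Section 4.4 rests on the MMRM.

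**Planning figures (Section 2.3).** The inputs are a difference of 1.7 days, SD 6.29, two-sided alpha 0.05 and 90% power.

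- n per arm = 2 × (1.960 + 1.282)² × (6.29/1.7)² ≈ 288 by the normal approximation, against 289 in the SAP.
- Power at 289 is 90.1% (normal) or 90.0% (noncentral t).
- 289/(1 − 0.15) = 340.

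The stated figures reproduce, so SD 6.29 and 289 per arm are used below.

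**Baseline precision**

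- SE of a pairwise difference = 6.29 × √(2/289) = 0.523 day.
- 95% CI half-width = 1.96 × 0.523 = 1.03 days.

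**Loss of precision without region.** Let p be the US share and d the difference in mean change between regions, given the other covariates. Both are assumptions, because the SAP gives neither. With 6.29 as the total SD, region accounts for a variance share s = p(1 − p)d²/6.29², and the SE ratio (omitted/included) is 1/√(1 − s).

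| p | d (days) | s | SE increase |
|---|---|---|---|
| 0.2 | 0.5 | 0.10% | 0.05% |
| 0.4 | 1 | 0.61% | 0.30% |
| 0.4 | 2 | 2.43% | 1.24% |
| 0.5 | 3 | 5.69% | 2.97% |

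Applied to the 1.03-day half-width, an increase of 0.05-3.0% is 0.001-0.03 day. If 6.29 is instead taken as the SD with region in the model, the ratio is √(1 + s), which gives 1.028 at p = 0.5, d = 3. The conclusion is the same.

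**Shift in the treatment difference.** This was simulated with 4,000 trials per scenario, 289 per arm, 1:1:1 blocks of three within two regions, one complete outcome per patient and a true difference of −1.7 days.

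| d, p | SE ratio | Mean absolute shift (days) | 95th percentile (days) |
|---|---|---|---|
| 1, 0.4 | 1.003 | 0.001 | 0.004 |
| 2, 0.4 | 1.01 | 0.002 | 0.007 |
| 3, 0.5 | 1.03 | 0.003 | 0.011 |

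No bias appeared in this complete-data setting. If the strata of country, sex and medication use left a 0.5-2 percentage-point imbalance in region share between arms, a regional difference of 1-3 days would move the estimate by 0.005 × 1 = 0.005 to 0.02 × 3 = 0.06 day, against a planned effect of 1.7 days.

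**Shift in LS means.** LSMEANS as coded weights the levels of a CLASS effect equally once it is in the model. Adding region therefore moves every arm by |0.5 − p| × d. At p = 0.4 and d = 1-2 this is 0.1-0.2 day. Over the full assumed range it is 0 (p = 0.5) to 0.9 day (p = 0.2, d = 3). The shift is common to all arms and cancels from the differences.

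**The case against.** The strongest reply is that this is a dropped word, not an open choice of model. The text is explicit, REGION has no purpose in CLASS unless it enters MODEL, and the parallel ANCOVA code includes it. The code is also a template with placeholder dataset names. On this reading a competent programmer would add the term, and the numerical effect is negligible for a supportive analysis.

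Much of that stands. Region was almost certainly intended, and the size is small. But Section 6.2.2 calls its code a sample, while Section 6.2.3.1 does not use that word for its own block. With no rule on text versus code, copying the block would be a reasonable reading.

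Three cautions on the figures also stand:

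- The upper ends (3% on the SE, 0.9 day on the LS means) come from extreme assumed inputs. A 3-day regional difference remaining after adjustment for baseline, sex, preventive use and years since onset would be nearly twice the planned effect.
- The simulation has one complete outcome per patient. It does not test the by-month estimates or months set to missing, so the absence of bias is shown only in that simpler setting.
- The LS means already weight sex and preventive use equally, so their level is not population-weighted even without region.

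**Conclusion.** The point holds as a minor inconsistency in operative code. Run as printed, the MMRM is not the model that the text specifies. It also differs in its covariates from the primary ANCOVA that it is meant to support, and the discrepancy carries into every analysis that reuses it.

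Sample size, alpha and the fixed sequence are untouched, and the multiple-imputation analysis keeps region. At a 40/60 regional split and a 1-2 day difference, the standard error grows by 0.3-1.2%. Stratified randomisation makes material bias in the treatment difference unlikely. These sizes rest on assumed regional inputs and on complete data. That the text and the code disagree rests on no assumption.

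**What to change.** Change the statement in Section 6.2.3.1 to `MODEL CHG=BASE YOD BMU SEX REGION TREAT MONTH TREAT*MONTH/S;`.

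Keep region wherever this MMRM is reused. For the endpoints that Section 6.4.2.1 analyses "for the following endpoints by week after the 1st dose of study drug", week takes the place of month. Section 6.5 says: "The ANCOVA analysis defined in Section 6.2.2 and MMRM analysis defined in Section 6.2.3.1 will also be applied to following subgroup populations analysis". There, a factor that is constant within a subgroup (sex in the by-sex subgroups, preventive use in the preventive-treatment subgroups) can be dropped. This is only tidying, since leaving it in does not change the treatment estimates.

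The cost is one word in the SAP code and the matching program, ideally before programming starts. No confirmatory analysis changes.

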6.2.3.2. Analysis with Multiple Imputation Method

Multiple imputation (MI) method will be applied to impute the monthly missing data. The data will be processed by the following steps.

- If a patient has partial e-diary data (i.e., <10 days) for a month, that month value will be considered missing before the MI procedure.
- For the patients in the active treatment group who are early terminated with reasons of adverse event or lack of efficacy, they will be assigned to placebo group so their missing values will be imputed using data from the placebo treated patients
- Run SAS PROC MI procedure to create 10 complete datasets.
- Within each imputed data set, for a patient who has partial, say X ($X < 10$) days, e-diary data in a month, the monthly value will be replaced by

$$\sum(\text{observed days of at least moderate severity}) + (28 - X) * \text{imputed value} / 28$$
- The monthly average number of headache days of at least moderate severity **during the 12-week period** after the 1st dose of study drug will be the average of month 1, month 2 and month 3 values.

Each dataset will be analyzed using the same ANCOVA model as described in Section 6.2.2. The LS means and standard errors from each analysis will be output to a SAS data set. SAS MIANALYZE procedure will be used to generate the final LS means (±SE) for the treatment

groups and the treatment differences (TEV-48125 - placebo) as well as p-values associated with treatment differences. The 95% confidence intervals for the treatment differences will also be constructed.

6.3. Secondary Efficacy Variables and Analysis

The secondary efficacy endpoints are listed in Section 2.2.2.

A migraine day will be endorsed when at least 1 of the following situations occur:

- A calendar day (0:00 to 23:59) demonstrating at least 4 consecutive hours of a headache endorsing criteria for migraine with or without aura
- A calendar day (0:00 to 23:59) demonstrating at least 4 consecutive hours of a headache endorsing criteria for probable migraine, a migraine subtype where only 1 migraine criterion is missing
- A calendar day (0:00 to 23:59) demonstrating a headache of any duration that was treated with migraine-specific medications (triptans and ergot compounds)

Migraine days will be derived based on the patient entered e-diary questionnaire as defined by ICHD-3 criteria [[Classification Committee of the IHS, 2013](#)] (see [Appendix B](#) for the logic of derivation).

6.3.1. Variable Definition

6.3.1.1. Electronic Headache Diary Data

The change from baseline in the monthly average number of days of secondary efficacy variables (e.g., migraine days, days with at least moderate severity, days of use of any acute headache medications etc.) *during the 12-week period* after the 1st dose of study drug will be derived similar to the primary variables using the e-diary data collected through the corresponding headache diary questions ([Appendix A](#)). The baseline values and the postbaseline values will be calculated using formula (3) and (1) respectively. *The change* is calculated as *postbaseline value – baseline value*.

The percent reduction in the monthly average number of headache days of at least moderate severity *during the 12-week period* after the 1st dose of study drug will be calculated by formula (4) in Section 6.1. The patient is considered as a responder if the percent reduction is 50% or more. If a patient is early discontinued from the study, he/she will be counted as a non-responder.

The change from baseline (run-in period) in the number of headache days of at least moderate severity *during the 4-week period* after the 1st dose of study drug will be derived similar to the primary endpoint using only the 1st month diary data. Since the patients randomized to both active treatment arms receive the same dose of TEV-48125 675-mg at their 1st dosing, their data will be combined for analyzing the endpoints *during the 4-week period* after the 1st dose of study drug.

6.3.1.2. HIT-6™ Headache Impact Test

Migraine related disability will be assessed using the HIT-6 (see [Appendix C](#)) completed at visit 2 before the 1st injection and end of study visit. Each patient will answer the HIT-6 questionnaire questions to measure the impact headaches that have on his/her ability to function on the job, at school, at home and in social situations. Each question is answered on the scale ranging with the following response options: 6 points (never), 8 points (rarely), 10 points (sometimes), 11 points (very often), and 13 points (always). The total score is obtained from summation of the 6 question points. The HIT-6 total score ranges between 36 and 78, with larger scores reflecting greater impact. If 1 or more items are missing, then the total score is missing.

6.3.2. Analysis of Secondary Efficacy Variables

An ANCOVA method, which is similar to the primary analysis setup, will be used for the analysis of the mean change from baseline in the monthly average number of days of secondary efficacy variables *during the 12-week period* derived from headache diary data. The model will include treatment, sex, region, and baseline preventive migraine medication use (yes/no) as fixed effects; the baseline values and years since onset of migraines as covariates. The LS means for the treatment groups, LS mean and 95% confidence intervals for the treatment differences (TEV-48125 – placebo), and associated p-values will be provided.

If a patient has less than 10 days of e-diary data entries after the 1st dose of study drug, the missing data handling method for the primary variable discussed in Section 6.2.1 will be applied for the monthly average number of days of secondary efficacy variables *during the 12-week period*.

Similar to the sensitivity analysis for the primary efficacy variable described in Section 6.2.3.1, an MMRM model will be implemented to estimate the mean change from baseline for the following endpoints by month and for overall 3 months after the 1st dose of study drug.

- mean change from baseline (28-day run-in period) in the monthly average number of migraine days
- mean change from baseline (28-day run-in period) in the monthly average number of days of use of any acute headache medications

LS means for the treatment groups, LS means and corresponding 95% confidence intervals for the treatment differences (TEV-48125 - placebo), and associated p-values will be calculated by month and for the overall treatment period.

The LS means \pm SE of e-diary efficacy variables estimated by MMRM will be plotted by month for each treatment group.

Cochran Mantel-Haenszel test stratified by baseline preventive migraine medication use (yes/no) will be used for analyzing the proportion of patients reaching at least 50% reduction in the monthly average number of headache days of at least moderate severity during the 12-week period after the 1st dose of study drug. The SAS Proc FREQ will be used to carry out this analysis.

The 2 active treatment groups data will be combined to compare with the placebo group by ANCOVA method for analyzing the mean change from baseline in the number of headache days of at least moderate severity during the 4-week period after the 1st dose of study drug.

Patients not receiving concomitant preventive medication constitute the sub-population who don't take any preventive migraine medications listed in APPENDIX B of the protocol during the study, ie, with baseline preventive migraine medication use = No.

The HIT-6 total score will be analyzed using the same ANCOVA method as described in Section 6.2.2.

For all relevant secondary endpoints, the normality of the residuals from each ANCOVA model will be checked using Shapiro Wilk's normality test. In case that the Shapiro Wilk's test has a p value ≤ 0.01 , Wilcoxon rank-sum test will be conducted as the primary analysis. The ANCOVA analysis will be considered as a supportive analysis.

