2.4.2. Blinding/Unblinding

This is a randomized study with stratification based on sex, country, and baseline preventive migraine medication use (yes, no). Each patient will undergo randomization in a 1:1:1 ratio within the stratum to which he or she belongs to receive 1 of the 2 TEV 48125 dose regimens or placebo, as assigned by the IRT. The IRT will manage initial drug supply, maintenance of adequate study drug supplies on site, and study randomization centrally. At the time of each study visit, the IRT will be queried, and site personnel will retrieve and administer a 1.5 mL volume from each syringe contained in the appropriately numbered kit(s).

The sponsor, investigators, study staff (except for staff involved in bioanalytical analyses), and patients will be blinded to treatment assignment. A computer-generated master randomization list will be provided to drug packaging facilities. Packaging vendor(s) will package active drug and placebo into single-visit kits according to Good Manufacturing Practice procedures. Kits will be identical in appearance and contain 1 prefilled syringe with active drug or placebo. Adequate

kit supply for upcoming study visits will be managed by IRT and kept (refrigerated at 2°C to 8°C) on site.

In case of a serious adverse event or pregnancy, or in cases when knowledge of the study drug assignment is needed to make treatment decisions, the investigator may unblind the patient's drug assignment as deemed necessary, mainly in emergency situations. Individual treatment codes, indicating the treatment randomization for each randomized patient, will be available to the investigator(s) and/or pharmacist(s) at the study center via the IRT, both via telephone and internet. If possible, the sponsor should be notified of the event prior to breaking of the code. If this is not possible, the sponsor should be notified immediately afterwards, and the patient's drug code assignment should not be revealed. Breaking of the treatment code can always be performed by the site without prior approval by the sponsor.

When a blind is broken, the patient will be withdrawn from the study, and the event will be recorded onto the CRF. The circumstances leading to the breaking of the code should be fully documented in the investigator's study files and in the patient's source documentation. Treatment assignment should not be recorded in any study documents or source document.

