4.3. Region of Pooled Countries

The countries will be pooled to 2 regions as [Table 2](#) for the analysis.

Table 2: The Region of Pooled Countries

Region	Country
United States	United States
Other	Japan, Czech Republic, Poland, Russia, Canada, Spain, Israel, Finland

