6.4.2.6. Patient's Global Impression of Change Scale

The percentage of patients' dichotomous scale of " Yes" or "No" rated by PGIC assessments at 4-week after each dose will be analyzed by Cochran Mantel-Haenszel test stratified by baseline preventive migraine medication use (yes/no) as described in Section 6.3.2.

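### The responder and PGIC tests stratify by preventive use only and leave out sex and region: valid, but a small and avoidable loss of power

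*SAP*

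**What the plan says.** **Randomisation.** SAP Section 2.4.2: "This is a randomized study with stratification based on sex, country, and baseline preventive migraine medication use (yes, no"). Sections 2.1 and 7.2 name the same three factors.

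**Continuous endpoints.** The primary ANCOVA in Section 6.2.2 uses all three, with country reduced to region: "The model will include treatment, sex, region (Table 2), and baseline preventive migraine medication use (yes/no) as fixed effects". Section 6.3.2 repeats this for the secondary diary endpoints: "The model will include treatment, sex, region, and baseline preventive migraine medication use (yes/no) as fixed effects". Section 4.3 explains the coding: "The countries will be pooled to 2 regions", namely the United States and all other countries.

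**Binary endpoints.** Section 6.3.2 uses one factor for the 50% responder endpoint: "Cochran Mantel-Haenszel test stratified by baseline preventive migraine medication use (yes/no) will be used for analyzing the proportion of patients". Section 6.4.2.1 does the same for the exploratory responder endpoints: "Cochran Mantel-Haenszel test stratified by baseline preventive migraine medication use (yes/no) will be implemented for analyzing the responder type of exploratory efficacy endpoints". Under Section 6.4.2.6 the dichotomised PGIC "will be analyzed by Cochran Mantel-Haenszel test stratified by baseline preventive migraine medication use (yes/no) as described in Section 6.3.2".

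**Place in the testing order.** In Section 4.4 the 50% responder comparison is step 4 for 675/225/225 mg and step 7 for 675 mg/placebo/placebo. Once a comparison has p > 0.05, nothing after it is interpreted inferentially.

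The SAP gives no reason for leaving sex and region out of the CMH. It plans no analysis of the responder endpoint that adjusts for them.

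**The concern.** Within Section 6.3.2, the same diary variable is adjusted for sex, region and preventive use when analysed as a mean change, but only for preventive use when dichotomised. Stratified randomisation balances the arms on sex and country. If those factors predict response, that balance lowers the true variance of the treatment comparison. A test that ignores them still uses the larger variance, so it can be slightly conservative and lose some power.

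Step 4 is where this counts. A miss there closes steps 5 to 13, starting with the second regimen's comparison on the primary endpoint. The sample size in Section 2.3 was set for a mean difference in days, and no power is stated for the responder endpoint. The exploratory responder and PGIC analyses gate nothing, so for them the issue is consistency and a little precision.

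**Working it through.** **1. The plan's own figure.** Section 2.3 gives a difference of 1.7 days, SD 6.29, alpha 0.05 and 90% power.

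n per group = 2 × (1.960 + 1.282)² × 6.29² / 1.7² = 288 after rounding up; the SAP states 289. Power at 289 is 0.901 (0.900 with the noncentral t). With 15% discontinuation, 289 / 0.85 = 340. The figure reproduces, but it concerns the continuous primary endpoint and does not depend on the CMH strata.

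**2. The test.** For stratum k with N_k patients, n_1k active, n_0k placebo, r_k responders and a_k active responders:

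CMH = [Σ(a_k − n_1k r_k / N_k)]² / Σ[n_1k n_0k r_k (N_k − r_k) / (N_k² (N_k − 1))], rejecting above 3.8415.

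The planned version has 2 strata (preventive use). The alternative has 2 × 2 × 2 = 8 (sex, region, preventive use).

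**3. Simulation.** From the SAP: 340 per arm, randomisation within sex × country × preventive use, nine countries in two regions, two-sided 0.05. Assumed, because the SAP gives no values: placebo response about 25%, treatment odds ratio (OR) 1.6, 87% women, 60% United States, 25% on preventive medication (the SAP caps this at 30%), and permuted blocks. There were 4000 runs per setting, with both tests applied to the same simulated trials.

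| OR for sex and for region (preventive use) | Type I error, 2 strata / 8 strata | Power, 2 strata / 8 strata | Power change, points |
|---|---|---|---|
| 1 (1) | 0.0515 / 0.0518 | 0.802 / 0.801 | −0.1 |
| 1.5 (0.7) | 0.0462 / 0.0475 | 0.797 / 0.801 | +0.4 |
| 2 (0.5) | 0.0480 / 0.0522 | 0.781 / 0.789 | +0.8 |
| 3 (0.5) | 0.0480 / 0.0540 | 0.760 / 0.780 | +2.0 |

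The Monte Carlo standard error of a type I error rate is √(0.05 × 0.95 / 4000) = 0.0034, so the largest value, 0.0540, lies about 1.2 standard errors above 0.05.

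**4. Other assumptions.** With 85% women, 55% United States, 25% preventive users, 20% placebo response, treatment OR 1.6 and preventive-use OR 1.5 (5000 runs), the power change was −0.1 points with no sex or region effect, +0.4 at ORs of 1.5, +0.6 at 2, and +1.9 at 2 and 3. The planned test's type I error was 0.050 at ORs of 2 and 3, and 0.044 at 3 and 3.

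A further set of 6000 runs, also with assumed rates, gave −0.1, +0.3, +1.2 and +1.7 points for the same four settings, and +3.3 at ORs of 3 and 3. Type I error ranged over 0.040–0.050 for the planned test and 0.049–0.053 with 8 strata.

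**5. Sparseness.** Under the step 3 mix, the smallest of the 8 strata (men, other region, on preventives) holds 0.13 × 0.40 × 0.25 × 680 = about 9 patients in a two-arm comparison. With country instead of region there are 2 × 9 × 2 = 36 strata. If the eight other countries were of equal size, the corresponding cell would hold about 9 / 8 = 1.1 patients.

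**The case against.** The strongest reply is that nothing here is wrong. The strata are pre-specified, consistent across three sections, and include one randomisation factor; omitting the others does not inflate type I error. This stands, and it limits the point to efficiency.

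The gain is negligible unless sex and region are strongly prognostic for response, and the SAP offers no evidence that they are. This also stands. With no prognostic effect the change is −0.1 points, which is simulation noise.

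The proposed strata do not reproduce the randomisation, which is by country, or the full ANCOVA, which also carries the baseline value and years since migraine onset. That is correct, but pooled region is the coding the SAP already uses, and it avoids the near-empty cells that country would create.

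The contrast with the ANCOVA is conditional. If the Shapiro-Wilk p-value is ≤ 0.01, Sections 6.2.2 and 6.3.2 switch to a Wilcoxon rank-sum test with no strata described, and the CMH would then be the more adjusted test. That is true, but it shows no drawback to fuller stratification of the CMH.

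A reader might infer from the mismatch that the responder tests are invalid, or that the SAP contradicts itself. The documents do not support either reading. A CMH on a subset of the randomisation factors keeps its error rate at or below nominal, and the SAP nowhere commits to using every randomisation factor in every test.

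**Conclusion.** The CMH for steps 4 and 7, the exploratory responder endpoints and PGIC uses one of the three randomisation factors, without a stated reason. The planned test is valid, and conservatism appears only under strong prognostic effects.

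The loss of power is about 0 points if sex and region are not prognostic, under 0.5 points at odds ratios of 1.5, and about 1 to 3 points at odds ratios of 2 to 3. All of these sizes rest on assumed response rates, treatment effect and population mix.

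A reader might also infer that the gate at step 4 makes this a serious threat to the second regimen. It does not: the chance of reaching step 5 falls by roughly the same few points at most, and the gate comes from the testing sequence, not from the strata. This is a minor, free improvement.

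**What to change.** Before unblinding, amend Sections 6.3.2, 6.4.2.1 and 6.4.2.6 so that the CMH is stratified by sex × two-level region (Table 2) × baseline preventive use, giving 8 strata. These are the categorical factors of the ANCOVA. Change all three sections together, because Section 6.4.2.6 refers back to Section 6.3.2. Use the pooled region, not country.

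The cost is one change to the PROC FREQ TABLES statement and three short wording changes. Some male strata will be small, which the CMH tolerates because it pools across strata; type I error stayed close to nominal in the simulations. If the sponsor prefers to keep preventive use alone, the SAP should say why and add the 8-stratum CMH as a sensitivity analysis for the 50% responder endpoint.
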